After consenting by a research team member in person or via telephone, review of the web-based Sickle Cell Decision Aid will be reviewed with participants, age ≥ 8 years with sickle cell disease and parents/legal guardians/caregivers of individuals (of any age) with sickle cell disease will be scheduled for an interview and review of the website within 6 weeks of consent. Additionally, stakeholders and healthcare providers may be recruited for participation.

Interviewers will demonstrate in-person or describe over the telephone use of the website, including navigation and the elements of the site. Participants will then be asked to navigate the site. As the participant navigates the site, the interviewer will ask the participants to describe thoughts about the site, including but not limited to ease of navigation, content and construction. Beta testing may be performed in-person or via telephone. Using qualitative iterative process, questions design will be analyzed after every 15-30 interviews, allowing for increased focus of questions based on themes and issues identified during ongoing analysis. Per qualitative data collection and analysis methods, this process allows for greater clarification of emerging themes and concepts. Interviews will take up to 60 to 90 minutes to complete. Interviews will be audio recorded and transcribed verbatim for later analysis. Interviews will be conducted in a private setting, away from parents, family, caregivers and clinical staff.

Demographic information will be collected including but not limited to age, gender, marital status, education level and role in sickle cell disease (patient, caregiver, stakeholder, provider). Additionally patients and parents/legal guardians of patients will be asked to self-report information regarding themselves or the patient they care for including but not limited to patient age, gender, education level, marital status, genotype, insurance type, history of HLA typing, number of hospitalizations for sickle cell related complications in the past 2 years. No PHI will be accessed for these qualitative interviews.

Hindi Beta Testing

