3. Parents/caregivers will be directly responsible for care of child <18 years of age with sickle cell disease.
4. Health care providers will provide direct care to patients with sickle cell disease.
5. Participants will speak and read fluent Hindi for enrollment into the Hindi Beta testing portion of the study.

Testing of Decision Aid

1. Individuals with sickle cell disease ages 8 to 80 years, inclusive
OR
2. Parent/legal guardian of patients (age < 18 years) with sickle cell disease who are directly involved in decision making regarding sickle cell disease healthcare treatment
OR
3. Health care provider directly involved in care of individuals with sickle cell disease, including child of parent/legal guardian enrolled in study
4. Patients/parents/caregivers who have made a past decision to not obtain treatment of the considered option or who have not obtained treatment of the chosen option in past 12 months.
5. All participants will be able to comprehend English

6. Patients/Parent/Legal guardian will have access to the internet from iPad, smart phone or personal computer
7. Patients <18 years may participate in Testing of Decision Aid, Cohort B, if they have participated in the Qualitative Needs Assessment Interviews only if they complete the Needs Assessment Interview first.

Exclusion Criteria

Qualitative Needs Assessment Interviews

1. Family members/Individuals/Caregivers not directly involved in decision-making regarding sickle cell disease healthcare.
2. Family members/Individuals/Caregivers not directly involved in decision-making regarding healthcare for post-bone marrow transplant patients with sickle cell disease.
3. Adult patient/parent/legal guardian participant in Testing of Decision Aid aspect of this study
4. Healthcare providers who are not directly involved in care of sickle cell patients
5. Stakeholders who are not involved in any aspect of sickle cell disease

Testing of Decision Aid

1. Family Members/Individuals/Caregivers not directly involved in decision-making regarding sickle cell disease healthcare.
2. Patient/parent/legal guardian who has already made a decision to begin and has started the treatment option.
3. Parent/legal guardian of child who is participating in Cohort B of this study.
4. Child < 18 years of parent/legal guardian who is participating in Cohort A of this study and randomized to the control arm and not the decision aid arm.

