5. Spouse, significant other, or other family member involved in decision making for child <18 years if parent/legal guardian of child already enrolled into this study.

Total number of subjects to be studied (including those screened for eligibility) in Qualitative Needs Assessment Interviews and Beta Testing:

Up to 50. Sample size is dependent on data saturation during analysis and need for verification of findings.

Total number of subjects to be studied in Hindi Beta Testing

Up to 50 individuals will be consented for participation in the Hindi Beta Testing study. Sample size is dependent on data saturation during analysis and need for verification of findings.

Total number of subjects to be studied (including those screened for eligibility) in Testing of Decision Aid:

Cohort A: 120

Cohort B: 25

Cohort C: Up to 50 (depending on number of health care providers providing care to patient population in this study).

Sample Size Calculations for the Randomized Clinical Trial (Cohort A)

We assume that patient involvement is 30% with standard care and we can double this with the intervention. Based on 90% power and 0.05 significance level we will require 110 patients, 55 in each group for comparing 2 binomial proportions⁴⁴. To account for attrition we propose to recruit 120 patients, 60 in each group treatment group with 20 in each of 3 age groups.

Total Duration of Participation

Qualitative Needs Assessment Interviews: 6 weeks

Decision Aid Testing: Up to 12 months

Recruitment Methods

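### The trial's exclusion list does not bar adults who have already used the decision aid website in beta testing, so a control participant could enter pre-exposed

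*Combined protocol and SAP*

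**What the plan says.** Under *Study Design for Beta Testing*, the interviewer demonstrates or describes the website, and then "Participants will then be asked to navigate the site" while commenting on it. Sessions last up to 60 to 90 minutes. The Abstract and the aims place development and beta testing before the randomised trial.

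Patients aged 8 to 80 are eligible both for beta testing and for Testing of Decision Aid. Parents of affected children under 18 also qualify for both. The size of the interview and beta-testing component is "Up to 50. Sample size is dependent on data saturation during analysis and need for verification of findings".

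Under *Exclusion Criteria*, the list headed *Qualitative Needs Assessment Interviews* has as item 3: "Adult patient/parent/legal guardian participant in Testing of Decision Aid aspect of this study". Beta testing has no exclusion list of its own. The list for *Testing of Decision Aid* has five items, and none concerns a participant's own earlier use of the aid. The item closest to contamination is item 4, which bars a "Child < 18 years of parent/legal guardian who is participating in Cohort A of this study and randomized to the control arm".

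The sample-size section states: "We assume that patient involvement is 30% with standard care and we can double this with the intervention". It continues: "Based on 90% power and 0.05 significance level we will require 110 patients, 55 in each group", and "To account for attrition we propose to recruit 120 patients, 60 in each group treatment group with 20 in each of 3 age groups".

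**The concern.** The control condition in Cohort A is usual provider education without the website. An adult who has spent an hour or more navigating and discussing the site has already had the component that controls are meant to lack. If such a person is randomised to control and keeps some benefit, the control arm moves towards the intervention arm. The estimated effect on involvement, knowledge and decisional conflict then shrinks, and power falls.

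The plan would not reveal this afterwards. The listed entry data do not specify earlier use of the aid, although those lists are open-ended. Randomisation is subdivided by age group only. *Avoidance of bias* does not raise the issue, and no analysis without prior users is planned.

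The protocol does treat contamination as a threat elsewhere. It keeps the child of a control-arm parent out of Cohort B, and it opens the website to controls only after their final data collection. A control's own earlier use is a more direct route, and it is left open.

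**Working it through.** **Inputs from the protocol.** Control rate 0.30, intervention rate 0.60 (double), 90% power, significance level 0.05, 55 per arm required and 60 per arm recruited. Sidedness is not stated.

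**Reproducing the plan's figure.** Two-sided test, pooled variance under the null, no continuity correction:

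n per arm = [z₀.₉₇₅ √(2p̄(1−p̄)) + z₀.₉₀ √(p₁(1−p₁) + p₂(1−p₂))]² / (p₂−p₁)²

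With p̄ = 0.45: [1.960 × √0.495 + 1.282 × √0.45]² / 0.30² = 55.7, so 56 per arm against the stated 55. A one-sided test would give 46, so the two-sided reading is the one that fits.

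Power = Φ{[(p₂−p₁) − 1.960 √(2p̄(1−p̄)/n)] / √((p₁(1−p₁) + p₂(1−p₂))/n)}. With no exposed controls this is 89.6% at 55 per arm and 92.1% at 60.

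**Adding pre-exposed controls.** Let f be the share of controls who have already used the aid. The documents do not give f, so it is an assumption. Assume also full carry-over, meaning that an exposed control responds at 60%; this is the worst case. Then:

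- control rate = 0.30 + 0.30f
- difference = 0.30(1 − f)

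Example for f = 0.10 at 55 per arm: control rate 0.33, p̄ = 0.465, difference 0.27. Power = Φ[(0.27 − 1.960 × √(0.49755/55)) / √(0.4611/55)] = Φ(0.91) = 81.9%.

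| f | Exposed controls of 60 | Beta testers entering Cohort A (1:1) | Control rate | Difference | Power, 55 per arm | Power, 60 per arm |
|---|---|---|---|---|---|---|
| 0 | 0 | 0 | 30.0% | 30.0 points | 89.6% | 92.1% |
| 0.05 | 3 | about 6 | 31.5% | 28.5 points | 86.1% | 89.0% |
| 0.10 | 6 | about 12 | 33.0% | 27.0 points | 81.9% | 85.2% |
| 0.20 | 12 | about 24 | 36.0% | 24.0 points | 71.8% | 75.5% |

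With half carry-over, the control rate at f = 0.10 is 0.30 + 0.5 × 0.30 × 0.10 = 0.315. That is the 5% row.

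**How plausible each row is.** The 20% row needs about 24 entrants from an English pool of at most 50. That pool also holds interview-only participants, children, providers and stakeholders, most of whom could not enter Cohort A. Those who could must also be weighing a treatment that they have not started. The 20% row is therefore near-extreme; the 5% and 10% rows are the more useful illustrations.

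**The case against.** The strongest reply is that the protocol already means to keep adults out of both parts. Exclusion item 3 makes the interviews and the trial incompatible for adults. The inclusion heading and the sample-size heading both pair the interviews with beta testing, so the exclusion heading may simply have been shortened. Only patients under 18 get an express route into both parts, which would be unnecessary if adults could do both freely. This stands as evidence of intent. A reader might infer that the design knowingly admits exposed controls, and the documents do not support that. But the rule does not name beta testing, and it is not on the list used to screen trial entrants.

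The second reply concerns size, and it also stands. A reader might take the 72% power figure as a realistic prospect, but it combines full carry-over with near-extreme overlap. One beta-testing session is also less than the trial intervention, which gives personal access to the website with monthly follow-up, alongside provider education about a current decision.

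Two further inferences should be resisted:

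- **Hindi beta testing** (up to 50 more people) should not be added to the exposed pool. The documents do not say that it precedes the trial, and it requires fluent Hindi while the trial requires English comprehension.
- **A raised baseline among intervention participants** would matter only in a change-from-baseline analysis, and none is specified.

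**Conclusion.** The gap holds as a matter of text: nothing on the trial's exclusion list stops an adult who has already used the website in beta testing from being randomised to control. The direction of any bias is towards no effect. Whether it arises depends on beta testers enrolling, being allocated to control and retaining some benefit. The documents do not say how many would do so, and the make-up of the pool suggests few.

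On the worst-case assumption of full carry-over, 5% to 10% exposed controls would cost about 3.5 to 8 points of power at 55 per arm (89.6% to 86.1% or 81.9%), or about 3 to 7 points at 60 per arm (92.1% to 89.0% or 85.2%). Partial carry-over would cost less. The likely loss is modest, but the weakness is easily closed, and closing it fits the contamination safeguards that the protocol already has.

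**What to change.** Add a sixth item to the Testing of Decision Aid exclusions: *Adult patient, parent or legal guardian who has previously used the decision aid website, including in beta testing.* Check it at screening against beta-testing enrolment. The protocol keeps contact details and an identification key until the study is complete, so the check should be feasible, although no dedicated log of beta testers is described.

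The cost is one eligibility line, a check at screening and a slightly smaller recruitment pool. The sample size does not change: with prior users excluded, the planned 30% versus 60% contrast stands.

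If the sponsor prefers not to shrink the pool in a rare disease, the minimum alternative is to record earlier use at entry and pre-specify a sensitivity analysis without prior users. That would show the dilution but would not prevent it.

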2. Does the use of a decision aid result in improvement of patient knowledge, patient involvement in the decision, the congruence of their decision with their values and preferences?
3. Is the Hindi version understandable and useable by patients?

Expected Outcomes:

1. Collection and analysis of qualitative interviews using an open-ended semi-structure interview guide will provide understanding of patient and parent/caregiver knowledge, expectations, values, barriers and needed support that needs to be provided in a decision aid tool.
2. Based on the goals of the decision aid to provide accurate information to patients and caregivers about the risks and benefits of various treatments and to enable them to make informed and involved therapeutic decisions based on their values, preferences and stated goals we propose the following outcomes:
 - a) Impact on patient knowledge and understanding of treatment risks and benefits. Patient knowledge will be tested by using a knowledge questionnaire. Since knowledge is different from understanding we will design questions that test understanding e.g., if they understand the concepts and meaning for e. g., of an 80% survival by using different scenarios.
 - b) Impact of the decision aid on the decision making process and on the treatment decision, including the extent of patient involvement, the specific decision made, satisfaction with the decision-making process and with the decision. Patient involvement in decision making will be tested using a Patients' Perceived Involvement in Care Scale^{38,39}.
 - c) Psychological impact of decision aids on decisional burden, decisional conflict and decisional regret. Decisional conflict will be measured using a decisional conflict scale. Decisional conflict is evaluated using a validated decisional conflict scale^{40,41}. Decisional regret will be evaluated by using a validated decision regret scale⁴². Decisional burden will be evaluated using a validated decision burden scale⁴³.
 - d) Uptake, adherence and satisfaction with therapeutic option discussed. Within 4 months following discussion with the physician/healthcare provider we will also survey patients to determine their uptake, adherence with, and satisfaction with, the therapeutic option discussed.
3. The Hindi version of the decision aid will be comprehensible and useable as demonstrated by beta testing.

Methods

Study Design for Qualitative Interviews Decisional Needs Assessment

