For **Cohort A**, we will use a randomized controlled trial for the use of a web based decision aid to give patients with sickle cell disease and parent/legal guardian of children with sickle cell disease accurate information about risks and benefits of therapies and enable them to make decisions based on their individual values and preferences. Participants will complete surveys before, soon after and within 4 months following their discussion with their health care provider to determine impact of the decision aid on knowledge, involvement in the decision and on decisional conflict, quality and uptake and adherence with the therapies.

For **Cohort B** we will use a mixed methods descriptive study design to determine the impact of the decision aid on quality and comprehension of information, and impact on daily life relating to management of sickle cell disease in patients <18 years of age.

Cohort C - To better understand the effect of the decision aid in decision making and patient involvement as reported by the physicians consenting these patients (child and adult) for treatment will be asked to participate in the study. Health care providers will not be randomized.

Randomization

After the consenting process is completed, adult participants will be assigned to **Cohort A** and will be randomized to the clinical trial control or intervention group. Further subdivision will be done by age, to include three age groups:

1. Parent/legal guardian of children (age group of child < 18 years)
2. Individuals with sickle cell disease =>18 years to <28 years
3. Individuals with sickle cell disease =>28 years

Participants <18 years will be assigned to **Cohort B** and will not be randomized.

Health care providers will be assigned to **Cohort C** and will not be randomized.

Cohort A

Consenting/Visit 1

After consenting in-person or via telephone, we will collect demographic information from adults with sickle cell disease including but not limited to age, gender, race, education, marital status, employment, religion, number of full and half siblings, as well as relationship, age and education of individual(s) who assists with sickle cell related healthcare decision making.

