We will collect demographic information from parent/legal guardian of children (<18 years of age) including but not limited to age, gender, race, education, marital status, employment and religion. Additionally we will collect demographic information about the child including but not limited to age, gender, race, education, number of full and half siblings). Additionally patients and parents/legal guardians of patients will be asked to self-report information regarding themselves or the patient they care for including but not limited to patient age, gender, education level, marital status, genotype, insurance type, history of HLA typing, number of hospitalizations for sickle cell related complications in the past 2 years. No PHI will be accessed.

Participants will be asked to complete the following study surveys at within 2 weeks following their office/clinic visit, questionnaires will be available in paper version and electronically:

- Acceptability of education (*8 multiple choice, 2 short answer*)
- Decision Self-Efficacy Scale (*11 multiple choice*)
- Decisional Conflict Scale (*16 multiple choice*)
- Values survey (*14 multiple choice, 6 fill in the blank*)
- Realistic Expectations (*multiple choice*)
- Preparation for Decision Making Scale (*10 multiple choice*)
- Knowledge Survey (*25 multiple choice*)
- Choice Predisposition and Decision (*1 multiple choice and 4 fill in the blank*)
- Stage of Decision Making (*10 multiple choice*)

Participants => 18 years of age will complete:

- Emotional distress Anxiety – short form 6a – participant version
- Depression – short form 6a – participant version
- Fatigue – short form 6a – participant version
- Pain interference – short form 6a – participant version
- Physical Function – short form 8b – participant version

- Ability to participate in social roles and activities – short form 6a – participant version

Participants of children <18 years of age will complete:

- Fatigue – short form 10 – parent proxy
- Mobility – short form 8 – parent proxy
- Peer relations – short form 7 – parent proxy
- Anxiety – short form 8b – parent proxy
- Depressive symptoms – short form 6b – parent proxy

It is anticipated that these surveys will take 20-30 minutes to complete within 2 weeks following each visit. Surveys may be available via paper version and electronically.

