Participants in Cohort A who are assigned to the control group will receive education regarding treatment consideration from their healthcare provider/team as per standard practice (usual care).

Participants in Cohort A who are assigned to the intervention group will receive education regarding treatment consideration from their healthcare provider/team as per standard practice. Additionally, they will be provided access to the decisional aid and will be provided with a unique access ID and password for purposes of this study. Participants will receive follow-up monthly via telephone call and/or e-mail to verify ability to access and navigate through website.

Visit 2

Participants will be scheduled for the second research visit to coincide with the completion of education presented by the healthcare provider/team. Participants will be asked to complete the study surveys within 2 weeks following the office/clinic visit via paper version or on-line. Self-report information regarding themselves or the patient they care for will be updated relating to sickle cell disease management and complications since Consent/Visit 1. Participants will receive follow-up monthly via telephone call and/or e-mail to verify ability to access and navigate through website.

Visit 3

Participants will be scheduled for the final research visit within 4 months of the completion of education and discussion with their healthcare provider/team. Participants will be asked to complete the study surveys as well as either via paper versions or online within 2 weeks following this office/clinic visit:

- Decision Regret Scale (*5 multiple choice*)
- Additionally, a qualitative interview will be conducted with the participants within 4 weeks of visit 3 to evaluate the extent to which the method of educational tools (standard practice or decision aid) helped the participant to recognize that a decision needs to be made regarding treatment of sickle cell disease, to understand the values that affect the decision, and understand if and how these values were addressed with the health care provider. Interviews will take approximately 30-45 minutes for completion. Interviews will

be audio recorded and transcribed verbatim for later analysis. Interviews will be conducted in a private setting, away from family members and clinical staff.

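### The only powered outcome, patient involvement (30% vs 60%), has no scheduled instrument, no rule for who counts as involved and no comparison visit

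*Combined protocol and SAP*

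**What the plan says.** **Power statement.** The section Sample Size Calculations for the Randomized Clinical Trial (Cohort A) states: "We assume that patient involvement is 30% with standard care and we can double this with the intervention". It continues: "Based on 90% power and 0.05 significance level we will require 110 patients, 55 in each group", for a comparison of two binomial proportions. Recruitment is raised to 120 (60 per group) for attrition. No other outcome has a power calculation.

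**Instrument.** Expected Outcomes 2(b) says involvement in decision making will be tested with the Patients' "Perceived Involvement in Care Scale". No other section names a patient-completed instrument for it.

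**Intent to collect.** Study Design for Testing of Decision Aid says Cohort A is surveyed before, soon after and within 4 months of the provider discussion, "to determine impact of the decision aid on knowledge, involvement in the decision and on decisional conflict", among other outcomes.

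**Survey lists.** Consenting/Visit 1 introduces its list with "Participants will be asked to complete the following study surveys at within 2 weeks following their office/clinic visit". Visit 2 refers back to that list: "Participants will be asked to complete the study surveys within 2 weeks following the office/clinic visit via paper version or on-line". At Visit 3 participants are to "complete the study surveys as well as either via paper versions or online", followed by the Decision Regret Scale and an interview. The Cross-Over section has its own full list.

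**Provider report.** Cohort C is described as addressing "patient involvement as reported by the physicians consenting these patients", but the only Cohort C form listed is a physician rating of the patient's readiness to decide.

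**The concern.** A comparison of 30% with 60% needs three things: an instrument that is administered, a rule that sorts each participant into involved or not involved, and a visit at which the sorting is done. The plan names an instrument but does not schedule it, and it gives neither the rule nor the visit.

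Staff who follow the lists would not collect the named measure. It could not be recovered well afterwards, because Avoidance of bias itself relies on surveys given within days of the provider interaction to limit recall error. If the scale is collected after all, the cut-off and visit remain open and could be settled with results in hand, so neither the false-positive rate nor the stated power would be controlled for that comparison.

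It is also unclear what standing the outcome has. No section calls involvement primary. The overarching hypothesis names knowledge, perception of risks and benefits, and decisional conflict. Aim 2 lists involvement beside knowledge and decision-making quality.

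**Working it through.** **1. Instruments named against instruments listed**

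| Construct in Expected Outcomes 2 | Visit 1 list (also used at Visit 2) | Added at Visit 3 | Cross-Over list |
|---|---|---|---|
| Knowledge | yes | – | yes |
| Patient involvement scale | **no** | **no** | **no** |
| Decisional conflict | yes | – | yes |
| Decision regret | no | yes | yes |
| Decision burden | no | no | no |

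The Visit 1 list has nine decision instruments plus health short forms. The Cross-Over list repeats all nine and adds Decision Regret. Cohort B has a self-efficacy scale and pediatric short forms; Cohort C has the readiness form. The involvement scale is in none of them. These lists are itemised, most of the decision instruments with item counts, and do not carry the open-ended wording the protocol uses for demographics.

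**2. Rule and visit.** No section gives a score, item or answer that makes a participant involved. Three survey times exist, but none is tied to the 30% vs 60% comparison. Analytic Methods refers back to endpoints as already defined; for involvement no definition precedes it.

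**3. The plan's own sample size.** Inputs from the sample size section: p1 = 0.30, p2 = 0.60, power 90%, alpha 0.05. Sidedness is not stated; two-sided is assumed. Pooled-variance normal approximation, with p̄ = 0.45:

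n per group = [1.960·√(2·0.45·0.55) + 1.282·√(0.30·0.70 + 0.60·0.40)]² / 0.30²

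= (1.379 + 0.860)² / 0.09 ≈ 55.7, so 56 against the stated 55.

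Power at 55 per group = Φ[(0.30·√55 − 1.379) / 0.671] = Φ(1.261) = 89.6%. At 60 per group it is 92.1%. The stated figure reproduces; the one-sided version gives 46 per group and does not.

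**4. How far power depends on the missing rule.** The documents give no rates other than 30% and 60%, so both models below are assumptions. Both use 55 per group and the same formula.

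- *Constant shift on a normal score.* The shift that turns 30% into 60% is Φ⁻¹(0.60) − Φ⁻¹(0.30) = 0.253 + 0.524 = 0.78 SD. Moving the cut-off then changes both rates.
- *Doubling.* The intervention rate is always twice the control rate.

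| Control rate | Power, constant shift | Power, doubling |
|---|---|---|
| 10% | 78% | 31% |
| 20% | 87% | 63% |
| 25% | 89% | 78% |
| 30% | 90% | 90% |
| 40% | 90% | 99.5% |
| 50% | 88% | not computed |
| 60% | 84% | not possible |
| 70% | 77% | not possible |
| 80% | 65% | not possible |

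Under a constant shift, power is nearly flat for mid-range cut-offs. Under doubling, it falls quickly when the control rate is below 30%.

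**The case against.** The strongest reply is that this is a clerical slip. The intent to measure involvement is explicit in two places, the survey times are stated, and the Visit 3 sentence is visibly broken, so text may have been lost there. The Cross-Over list is weak corroboration: it follows a website review by controls with no new provider discussion scheduled, so an involvement-in-care scale may have been left out on purpose. A list slip is therefore plausible, and involvement as such is not wholly unscheduled; what is missing is the named scale and the visit that carries the comparison. But restoring the scale would supply neither the yes/no rule nor that visit.

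Other sources might carry the outcome. Significance speaks of the proportion of people passive in decision making, so 30% may come from a single item. Preparation for Decision Making, Stage of Decision Making or another listed instrument may touch on involvement; their items are not shown. Cohort C is meant to capture involvement as providers see it, and Analytic Methods plans to turn qualitative data into numbers. Yet no section assigns any of these to the 30% vs 60% outcome. The Cohort C form concerns readiness and has no scoring rule, and no rule is given for coding involvement from interviews.

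Finally, the power table rests on assumed models, and the constant-shift model is calibrated to the same 30% and 60%. That is right: the table shows only that the stated power is conditional on the missing definition.

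**Conclusion.** The concern holds and must be fixed. The only powered outcome in Cohort A cannot be derived from the plan as written: its named scale is in no survey list, and no section gives a classification rule or deciding visit. The first gap may be a drafting slip; the other two remain on any reading.

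There is no sample size error. The stated 55 per group gives 89.6% power for 30% vs 60% (two-sided 0.05, normal approximation). That figure applies only to a definition of involved that yields about those rates. Under the assumed models, power is 87–90% for control rates of 20–50% with a constant shift, but 63% at 20% vs 40% if the rate merely doubles. The main defect is the uncollected, undefined outcome, not the power figure.

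**What to change.** Reconcile Expected Outcomes 2(b), the Cohort A study design and the sample size section with the Cohort A survey lists:

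1. Add the involvement scale to the Cohort A surveys, at least at the post-intervention visit used for the comparison, and complete the Visit 3 sentence.
2. State before analysis the rule that classifies a participant as involved, the visit at which it is applied, and why 30% under standard care is plausible on that rule.
3. Say which outcome is primary, since the hypothesis and the power statement point to different ones.

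If the scale is not to be collected, tie the power statement to a listed instrument and restate it. For a two-sample t-test at 90% power and two-sided 0.05, unadjusted, 55 per group detects about 0.62 SD and 60 per group about 0.60 SD. The documents give no expected effect on any listed scale, so the sponsor would have to state one.

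A minor related item: schedule the decision burden scale, which is also in no list, or remove it from Expected Outcomes 2(c).

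Restoring the scale costs one questionnaire, of a length the documents do not give, on top of a 20–30 minute battery, plus a short definition. The sample size stands if the rule supports 30% vs 60%. Using a listed instrument adds no questionnaire but may change the sample size.
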